## 1.0 BACKGROUND AND RATIONALE

### 1.1 Study Synopsis

We propose a prospective study to assess completion and performance of the following novel invasive cervical cancer (ICC) screen-and-treat algorithm among 625 HIV-positive women and 625 HIV-negative women in Lilongwe, Malawi: 1) rapid testing of self-collected vaginal brush for primary high risk (hr)-human papillomavirus (HPV), 2) same-day visual inspection with acetic acid (VIA) for women who are hr-HPV positive, and 3) thermocoagulation for VIA positive/ablation-eligible (by cervical colposcopy) women. This innovative strategy links two new technologies (Xpert HPV and thermocoagulation) with self-collected brush. It has not been rigorously evaluated among women, including HIV-positive women at highest risk for ICC. We hypothesize that >90% of women who are HPV-positive will have VIA performed same-day and that >90% of women who are VIA-positive/ablation-eligible (by colposcopy) will have thermocoagulation performed the same day.

### 1.2 Background

Invasive cervical cancer (ICC) is the 2nd most common cancer among women living in low-and-middle-income countries (LMICs), where 84% of the 445,000 new cases diagnosed in 2012 occurred. That same year, 270,000 women died from ICC, with >85% of these deaths occurring in LMICs. ICC is preventable with HPV vaccination, cervical cancer screening, and treatment of cervical dysplasia. However, LMICs have relatively poor utilization of these prevention strategies because they are difficult to access and implement, and require trained providers in settings where major shortages of skilled healthcare workers already exist. These challenges are compounded in Sub-Saharan Africa (SSA), the epicenter of the HIV epidemic, since HIV-positive women have >20-fold increased risk of ICC than HIV-negative women. ICC is the most common cancer among women in SSA and Malawi, with the burden disproportionately borne by HIV-positive women.

Malawi has the world's highest ICC mortality and is one of the world's poorest countries. Malawi's estimated HIV prevalence is 11% among females age 15-49 years, and HPV prevalence among HIV-positive women is estimated at 39%. Due to the challenges of implementing an HPV vaccination program, the HPV vaccine is not readily available in public programs in Malawi. Even if widespread HPV vaccination of girls is achieved in Malawi, millions of Malawian females will remain unvaccinated or age ineligible since only girls aged 9-13 years will be vaccination-eligible, and a subsequent decline in ICC incidence will not occur for decades, leaving millions of Malawian women vulnerable to developing ICC.

### 1.3 Purpose and Rationale

For LMICs, the World Health Organization (WHO) preferentially recommends an ICC screening approach of: 1) hr-HPV testing, 2) triage of hr-HPV positive women by VIA, and 3) cryotherapy treatment for VIA positive/ablation-eligible women (see definition below). Malawi adopted an approach of VIA screening and cryotherapy treatment in 2004, since rapid and inexpensive hr-HPV testing was not yet available. Cryotherapy has been challenging to implement, with <25% VIA centers with established cryotherapy and >50% of women who require treatment not receiving it, largely due to the high cost of refrigerant gas and heavy gas cylinder, which are difficult to obtain and transport. Loss-to-follow-up for VIA-positive women referred to centers with cryotherapy has also been a challenge. A screen-and-treat approach, i.e. same day screening and treatment at the same site, greatly reduces loss-to-follow-up.

Cervical thermocoagulation (aka cold coagulation) is an alternative ablative treatment for high-grade cervical dysplasia, known as cervical intraepithelial neoplasia (CIN) grade 2+ (i.e. CIN2 or more severe), which includes CIN2/3, carcinoma in situ (CIS), the precursors to ICC. It was first introduced in 1966 and used in the United Kingdom in the 1980s. Thermocoagulation uses thermosound probes, which are applied serially to destroy cervical lesions, using pre-selected temperatures of up to 120°C. In contrast to electrodiathermy, it produces no smoke, and therefore, no smell. A meta-analysis on the efficacy of thermocoagulation showed that cervical dysplasia cure rates were comparable to other excisional and ablative treatment methods in use worldwide. Despite reports of efficacy against all grades of cervical dysplasia and infrequent minimal side effects, thermocoagulation has been infrequently used since the 1980s because it was replaced by excisional methods that are readily available in high-income countries, and its use was never expanded to LMICs. In the same meta-analysis, none of the studies were from SSA, and all studies evaluated the use of thermocoagulation among physicians, mostly gynecologists, which is impractical for countries such as Malawi, which has less than 20 trained gynecologists for a country of 19 million. However, thermocoagulation is the most implementable treatment modality for CIN2/3 for LMIC, due to ease of use by mid-level providers, and the previously-mentioned challenges faced with cryotherapy. Currently, second-generation Liger Thermocoagulator (Lehi, UT), a handheld and battery-operated thermocoagulation device that can treat around 20–30 women per battery life and which takes 20–40 seconds per treatment making it mobile and attractive for use in LMICs is available. However, there are limited data on the efficacy of thermocoagulation in SSA, where treatment is typically done by mid-level providers (rather than gynecologists), and where HIV prevalence is high. Despite this, SSA countries including Malawi have started adopting thermocoagulation for treatment of cervical dysplasia, due to challenges with cryotherapy, which are limiting availability of treatment for women who screen positive.

The Xpert HPV Assay (Cepheid, Inc., Sunnyvale, CA), is a qualitative real-time polymerase chain reaction assay that uses disposable cartridges to detect DNA from 14 different hr-HPV strains. The assay is run on the Cepheid GeneXpert System, which is a scalable instrument platform that can run simultaneous but asynchronous assays for the same or different assays, depending on the cartridge. Unlike previous HPV assays, which required skilled laboratory personnel, batching of multiple samples, and several hours to complete, the Xpert HPV Assay allows for a single sample to be run, with results within 1-2 hours of testing. The Cepheid GeneXpert System can be used for point-of-care testing for HPV, tuberculosis (TB), trichomonas, gonorrhea, chlamydia, and group B streptococcus. Given its multiple uses and rapid turnaround time, the Cepheid GeneXpert machines have recently become widely available in SSA including Malawi, where it is currently used for point-of-care TB testing. Performance of the Xpert HPV Assay in both general screening populations and HIV-positive populations is comparable to other commercially-available HPV assays, with similar sensitivity and specificity, even among self-collected brush.. Furthermore HPV testing on self- or clinician-collected vaginal samples is more sensitive than VIA for the detection of CIN2+, and ICC. Introduction and scale-up of HPV screening tests is now one priority action in the International Federation of Gynecology and Obstetrics (FIGO) Global Declaration on cervical cancer elimination. Combining the use of Xpert HPV rapid testing and novel strategy of self-collected vaginal specimen for HPV testing could improve women's screening participation as it avoids an initial pelvic exam, allows for same-day HPV results, with similar sensitivity and specificity as provider-collected vaginal specimen for detection of CIN2+, and is in line with the FIGO global declaration on cervical cancer elimination.

Other novel screening methods may also allow for same-day screen-and-treat approaches. Recently, HPV DNA testing of urine samples has been investigated as a possible screening modality. Collecting urine samples is less invasive than cervicovaginal samples and urine HPV results seem to be correlated with cervical HPV results and pathology findings. There is limited experience with Xpert HPV testing of urine samples. Beyond DNA testing, methylation levels of several human genes and HPV genotypes have been found to be strongly associated with the development of CIN2/3 or ICC. Therefore, measuring methylation levels has potential use as both a primary screening method as well as a triage method to improve the specificity and positive predictive value (PPV) for CIN2+ detection in HPV-positive women. The S5 DNA methylation classifier combines testing for methylation of target regions of the human tumor suppressor gene EPB41L3 and the viral late gene regions of oncogenic HPV types 16, 18, 31, and 33. To date, the S5 has been validated as a triage method for HPV-positive women among largely HIV-negative women, with promising findings. The S5

classifier has not been validated with urine samples, which as discussed are less invasive to collect.

Mobile ODT EVA system developed by Mobile Optical Detection Technologies combines the functionalities of a colposcopy and digital camera. The EVA system is used for visual examinations and documentation in multiple clinical settings including examination of the cervix. The EVA system allows the storage of information captured by the device in an online secured, and Health Insurance Portability and Accountability Act (HIPAA) (HIPPAA)-compliant cloud storage which is hosted by Amazon web services. The EVA system is encrypted upon set-up, and a PIN number or password is used to access the phone. The system provides a platform for external quality assurance for findings identified during visual examination of the cervix.

We therefore plan to evaluate a novel screen-and-treat algorithm among women, including HIV positive women, in Lilongwe, Malawi for the detection and treatment of high-grade cervical dysplasia with the following combination of strategies: 1) rapid testing of self-collected vaginal brush for hr-HPV, 2) same-day VIA for women who are hr-HPV positive, and 3) thermocoagulation for VIA-positive/ablation-eligible (by colposcopy with Mobile ODT EVA system) women. This innovative approach has not yet been rigorously evaluated among women, including those living with HIV. Therefore, this study will provide essential data to inform national policy in Malawi and other LMICs where both HIV and ICC prevalence are high. If successful, our approach is arguably the most broadly-scalable strategy to optimize ICC screening in countries where the proportion of women screened remains low and ICC prevalence is high.

## **2.0 STUDY OBJECTIVES AND ENDPOINTS**

### **2.1 Primary Objectives**

- 2.1.1. To assess completion of a novel ICC screen-and-treat strategy among women in Lilongwe, Malawi, using self-collected vaginal brush for hr-HPV testing, followed by same-day VIA and thermocoagulation for HPV-positive/VIA-positive/ablation-eligible (by colposcopy) women.
- 2.1.2. To determine the 24-week efficacy of thermocoagulation among women, including HIV-positive women, with CIN2/3.

### **2.2 Secondary Objectives**

- 2.2.1. To evaluate performance of the proposed ICC screen-and-treat strategy among women, including HIV-positive women, by estimating overtreatment for women who are HPV-positive/VIA-positive/ablation-eligible, and undertreatment among HPV-positive/VIA-negative women.

2.2.2. To explore women's experiences with the proposed ICC screen-and-treat strategy.

### 2.3 Exploratory Objectives

## 3.0 PATIENT ELIGIBILITY

### 3.1 Inclusion Criteria

The study population will consist of female participants who meet the following eligibility criteria for the study:

- 3.1.1 Females  $\geq$  25 years of age at study entry and  $\leq$  50 years of age (per current Malawi National Cervical Cancer Control Program guidelines for screening).
- 3.1.2 Ability and willingness of participant to provide written informed consent.

A total of 625 of the study participants will be HIV-positive and must meet the additional criterion:

- 3.1.3 Females with known HIV-positive status, verified as follows:
  - 3.1.3.1. Rapid HIV test (e.g. Unigold Recombigen, Oraquick, Alere DetermineTM Combo)  
And confirmed by one of the following:
    - 3.1.3.2. Second antibody test by a method other than the initial rapid HIV and/or enzyme/chemiluminescent immunoassay (e.g. Unigold Recombigen, Oraquick, Oraquick, Alere DetermineTM Combo) or
    - 3.1.3.3. Plasma HIV-1 RNA viral load (Abbott RealTime HIV-1) or
    - 3.1.3.4. Bio-Rad Geenius

### 3.2 Exclusion Criteria

[figure not shown]
All female participants meeting any of the following exclusion criteria at baseline will be excluded from study participation:

[figure not shown]
- 3.2.1. Current or prior history of cervical, vaginal or vulvar cancer or dysplasia.
- 3.2.2. Current symptomatic sexual transmitted infection requiring treatment (women will be allowed to be in the study upon successful treatment)
- 3.2.3. Prior HPV vaccination.
- 3.2.4. Participants with known allergy to acetic acid.
- 3.2.5. Participants with a history of total hysterectomy.
- 3.2.6. Participants who are pregnant or plan on becoming pregnant during the study period.

3.2.7. Participants who are less than 12 weeks postpartum.  
 3.2.8. Participants with other illnesses that would limit compliance with study requirements or in the opinion of the investigator or designee, have a problem that would make participation in the study unsafe, or complicate interpretation of study findings.

## 4.0 STUDY PLAN

### 4.1 Schema

This is a single arm, prospective study of 1,250 women, comprising of 625 HIV-positive and 625 HIV-negative women, in Lilongwe, Malawi. The primary purpose of this study is to assess completion and performance of a novel ICC screen-and-treat strategy among women in Lilongwe, Malawi, using self-collected vaginal brush for hr-HPV testing, followed by same-day VIA and thermocoagulation for HPV-positive/VIA-positive/ablation-eligible (by colposcopy) women. We anticipate that all participants will be enrolled over 12 months and that active participation will continue for up to 30 weeks at most.

#### 4.2 Duration of Study

Study participants will have four scheduled study visits: Screening/Enrollment, Week 4, Week 24, and Week 28. At Screening/Enrollment, women will complete an interviewer-administered baseline questionnaire, urine pregnancy testing, HIV rapid finger stick testing, and blood for CD4+ T cell count and HIV-1 RNA testing for HIV positive participants, and will self-collect a vaginal brush for hr-HPV testing. Urine collected for pregnancy testing will also be sent for hr-HPV and S5 methylation testing (for research purposes only). HPV-positive women and every 10th consecutive HPV-negative woman will complete same-day VIA with colposcopically-directed cervical biopsy and endocervical curettage (ECC) (if lesion seen), and thermocoagulation if ablation-eligible by colposcopy. If no lesion is seen on colposcopy, the woman will have a cervical pap smear and ECC collected, and no thermocoagulation will be performed. Finally, women who are suspicious for cancer at VIA will undergo colposcopically-directed cervical

biopsies. All women who undergo speculum exam will undergo provider-collected cervical swab, which will be sent for hr-HPV and S5 methylation testing (for research purposes only).

All women who had cervical biopsy or cervical pap smear and ECC done at Screening/Enrollment will return at Week 4 for histology and/or cytology results. All women who had CIN1, CIN2, or CIN3 and underwent thermocoagulation will be asked to return for a follow-up visit at Week 24 post-treatment to assess for resolution of their HPV and cervical dysplasia. At Week 28 visit, women will receive their histology and/or cytology results and be referred as necessary.

#### **4.3 Study Details**

##### **Study site**

The study will be conducted at UNC Project-Malawi Tidziwe Centre.

##### **Recruitment**

We will recruit women from Family Planning clinics, Under-5 Clinics, Outpatient Departments, and ART clinics (for HIV-positive participants) at facilities in Lilongwe by conducting educational talks about cervical cancer and the study in their waiting areas. We will schedule a screening and enrollment visit for potential participants interested in joining the study at UNC Project-Malawi, which is within a 15-30 minute drive from the targeted clinics. There, women will be asked to provide written informed consent and screened for eligibility to participate in the study. Up to thirty women will be recruited for in-depth interviews (IDIs) about their experiences with the proposed screen-and-treat strategy. The HPV-negative women will be recruited at the Screening/Enrollment visit while the HPV-positive women may be recruited at the Screening/Enrollment visit or the Week 4 visit. Transport reimbursement will be provided to participants attending study visits to mitigate participants' expenses for the study-related visits.

##### **Screening & Enrollment**

Women will be enrolled in Lilongwe, Malawi, a city with a population of 900,000. Participants will complete an interviewer-administered baseline questionnaire to collect socio-demographic data and cervical cancer risk factors. Baseline evaluation will include urine pregnancy testing, HIV rapid finger stick testing, and blood for CD4+ T cell count and HIV-1 RNA testing for HIV-positive women. Urine samples collected for pregnancy testing will also undergo Xpert HPV testing and S5 methylation testing. These urine tests are only for research purposes and results will not influence patient management.

Women will receive simple instructions on how to self-collect a cervicovaginal sample with vaginal brush for hr-HPV testing in the research clinic, using well-validated, field-tested illustrated instructions that are comprehensible to low-literacy women. The self-collection kit will contain a vaginal brush and vial of

sample preservation solution. Participants will then collect this brush, which will be tested onsite using Xpert HPV testing. HPV-negative women will be advised to continue with routine ICC screening per Malawi Cervical Cancer Guidelines. HPV-positive women will complete same-day VIA, using 3-5% acetic acid on the cervix for at least 1 minute, then observing for color changes indicating the presence of a lesion, as described in the WHO IARC Manual. We will also perform same-day VIA on every 10th consecutive woman found to be HPV-negative to assess for possible underscreening with self-HPV testing.

All women who undergo speculum exam will have a provider-collected swab performed, which will be sent for hr-HPV and S5 methylation testing. The results from these tests will be used to help evaluate the validity of urine hr-HPV and S5 testing; they will not be used to influence patient management.

For all women who undergo VIA, we will determine if a woman is VIA-positive and ablation-eligible using colposcopy with Mobile ODT EVA system. Women who are VIA-positive will undergo colposcopically-directed biopsies of the acetowhite lesion, with at least 2 and up to 4 biopsies taken, as well as an ECC. If the woman is still considered to be ablation-eligible by colposcopy, she will then undergo thermocoagulation. Women who are VIA-negative will also undergo colposcopy, and at least 2 and up to 4 cervical biopsies and ECC if a lesion is seen at colposcopy. Thermocoagulation will also be performed on these women if they are found to have an ablation-eligible lesion on colposcopy. If no lesion is seen on colposcopy, the woman will have cervical pap smear and ECC collected, and no thermocoagulation will be performed. Women who are suspicious for cancer at VIA will undergo colposcopically-directed cervical biopsies. Whenever biopsy is indicated, we will perform at least 2 cervical biopsies on women because previous studies have shown that cervical biopsy is most sensitive when at least 2 biopsies are taken. During colposcopy, images of the cervix may be captured with the EVA system. These images will be stored only in password-protected and de-identified study databases, linked only to the study participant PID. The images will be used for internal quality assurance and may also be shared with the sponsor or other parties for research purposes.

For women to undergo thermocoagulation, we will consider them to be ablation-eligible if the following criteria are met at colposcopy: 1) cervical lesions are not suspicious for ICC; 2) cervical lesions are located entirely on the ectocervix; 3) cervical lesions are no more than 2-3 mm into the endocervical canal; 4) the entire squamocolumnar junction (SCJ) can be visualized; and 5) all visible lesions are deemed appropriate for thermocoagulation by the treating provider. Women with suspected endocervical dysplasia, CIS, or ICC will be referred for treatment at the Kamuzu Central Hospital (KCH), a public tertiary and teaching hospital Colposcopy Clinic on which campus UNC Project-Malawi is situated.

For the IDIs, up to 30 women will be enrolled at either the Screening/Enrollment visit or Week 4 visit (if they are HPV-positive). HPV-negative women will only be enrolled if they were not selected to undergo VIA. Participants will be consented for the IDIs separately from their main consent for the study. Women will primarily be recruited at check-out and all interviews will be conducted after women have completed the screen-and-treat algorithm. The IDIs will be conducted in the local language, Chichewa, in private rooms at UNC Project Malawi. Women will be offered the choice to have the interview conducted off site (e.g., in the comfort of their home or some private off site place, if they prefer). The interview will include use of an interviewer-administered questionnaire evaluating women's rating of their privacy, embarrassment, discomfort, pain, and confidence during the screening/treatment process. The IDIs will cover prior knowledge of cervical cancer, experience with the self-sampling, understanding of the results, and intention to share their screening experience with others.

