women who are HPV positive/VIA positive/ablation-eligible, and undertreatment among HPV positive/VIA negative women. All HPV positive women and every 10th consecutive HPV-negative woman will undergo VIA. During VIA, we will determine if a woman is VIA-positive and ablation-eligible. Women who are VIA-positive will undergo colposcopically-directed cervical biopsies and endocervical currettings (ECC). If the woman is still considered to be ablation-eligible by colposcopy, she will then undergo thermocoagulation. Women who are VIA-negative will also undergo colposcopy, but they will only have cervical biopsies and ECC performed if a lesion is seen on colposcopy. Following VIA, we will collect directed cervical biopsies and ECC from VIA positive women prior to thermocoagulation treatment if ablation-eligible by colposcopy, or cervical pap smear and ECC from VIA negative women if no lesion is seen at colposcopy. If a lesion is seen at colposcopy, VIA negative will also undergo colposcopically-directed cervical biopsy and ECC. We hypothesize that <25% of HPV positive/VIA positive women would have been overtreated (no CIN2+, but treated) and that <30% of HPV positive/VIA negative women would have been undertreated (CIN2+, but untreated).

Data analysis for secondary objective I: Overtreatment will be calculated as the proportion of HPV positive/VIA positive/ablation-eligible women who would have been treated with thermocoagulation based on their HPV and VIA findings alone (without colposcopy), but were found to have no CIN2+ on colposcopically-directed cervical biopsy or ECC at Screening/Enrollment. This proportion will represent the women with no lesions or low-grade lesions (CIN1) who would have been unnecessarily treated if we based the decision to perform thermocoagulation on HPV and VIA testing alone.

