Undertreatment will be calculated as the proportion of women with CIN2+ at Screening/Enrollment who were not treated or referred via our screening algorithm due to a negative HPV and/or VIA result. This proportion will represent the women with CIN-2+ who were missed by our HPV-and-VIA-based algorithm. For undertreatment, we will also evaluate the proportion of women who underwent thermocoagulation but were ECC positive for endocervical CIN2+, and therefore needed to be referred for further management since thermocoagulation does not adequately treat endocervical dysplasia. We have based our hypotheses on a recent review, which found that the pooled estimates for VIA sensitivity and specificity were 0.69 (95% CI 0.54-0.81) and 0.87 (95% CI 0.79-0.92), respectively, as well as from the high false positive rate for VIA found in our pilot study with nurses and clinicians in Malawi. These performance measures, however, were for primary screening, rather than as referral to treatment among HPV positive women.

In addition, to assess the potential for undertreatment of HPV-positive women, we will conduct VIA at Screening/Enrollment for every 10th women who is hr-HPV

negative. This sub-set analysis of HPV negative women undergoing VIA will allow us to control for potential verification bias. As all women will not be referred for verification by colposcopy, using only the histology results on HPV positive women to estimate disease burden could lead to biased inference. To correct for this verification bias, we will utilize the colposcopy results among the random sub-set of HPV-negative women to employ the maximum likelihood method proposed by Zhou. Estimates using this method are valid provided that the histology data are missing at random. This assumption means that for women with the same test results, those who were referred to colposcopy were similar to those that were not. Corrected CIN2+ burden will be estimated using maximum likelihood estimators (MLEs). This secondary objective is largely descriptive and, thus, formal power calculations are not made.

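### HPV-negative women are verified by a predictable every-tenth count, but the verification-bias correction treats them as a random subset; a concealed 1-in-10 draw would remove that risk from selection at almost no cost

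*Combined protocol and SAP*

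**What the plan says.** The selection rule appears in five places. Section 4.2 has "HPV-positive women and every 10 th consecutive HPV-negative woman will complete same-day VIA", and Section 4.3 (Screening & Enrollment) gives the purpose: "We will also perform same-day VIA on every 10th consecutive woman found to be HPV-negative to assess for possible underscreening with self-HPV testing". Section 5.1, footnote 3, and two paragraphs of Section 6.3 under secondary objective I repeat the one-in-ten count; the footnote and the later of the two paragraphs omit the word consecutive.

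For the analysis, Section 6.3 says "we will utilize the colposcopy results among the random sub-set of HPV-negative women to employ the maximum likelihood method". It makes validity depend on histology being missing at random, explained as: "for women with the same test results, those who were referred to colposcopy were similar to those that were not". The quantity at stake is defined there too: "Undertreatment will be calculated as the proportion of women with CIN2+ at Screening/Enrollment who were not treated or referred via our screening algorithm" because the HPV result, the VIA result or both were negative.

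The documents state no random start, random list, concealment, keeper of the count, or rule for a selected woman who declines. The indicators for VIA invitation and completion in Section 6.3 cover HPV-positive women only.

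**The concern.** Choosing HPV-negative women for verification is the one allocation step in this single-arm study. A fixed count tells whoever keeps it when the next selection falls. The order behind the count is also open: Section 6.3 records separate times for brush return, test start, test completion and delivery of the result. Section 1.3 notes that the platform "can run simultaneous but asynchronous assays", so those times could rank the same women differently and yield a different tenth woman.

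Section 4.3 describes the risk-factor questionnaire and HIV test before self-collection, so a woman's risk profile may be known when the slot falls. Selection brings a speculum examination, colposcopy, endocervical curettage and either biopsy or Pap smear, which gives a woman or a staff member some reason to avoid or seek it.

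The correction, as described, conditions on test results alone. If selection or completion is related to HIV status, symptoms or willingness, its assumption fails and nothing in the method reveals it. HIV status alone could matter: 625 − 313 = 312 of the 812 expected HPV-negative women (38%) are HIV-positive.

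**Working it through.** **Inputs from the plan.** Section 6.2: 625 HIV-positive women, 50% hr-HPV positive (313), 20% of those with CIN2/3 (63); 625 HIV-negative women, 20% hr-HPV positive (125), 10% of those with CIN2/3 (13). Section 6.3: VIA sensitivity 0.69 (95% CI 0.54–0.81), which the plan itself says comes from primary screening.

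**The plan's own figures.** 63 + 13 = 76 women with CIN2/3; 76 × 0.95 = 72 evaluable, of whom 63 × 0.95 = 60 are HIV-positive. These reproduce. The plan gives no figure for the size of the HPV-negative subset or for corrected undertreatment, so those are derived here.

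**Weight per verified woman.** HPV-negative women: 1,250 − 313 − 125 = 812. One in ten is about 81. Weight w = 812 / 81 = 10.02.

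**Corrected undertreatment** with k CIN2+ cases found among the 81:

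U(k) = [(1 − Se) × 76 + w × k] / (76 + w × k)

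With Se = 0.69, (1 − Se) × 76 = 23.56:

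- k = 0: 23.56 / 76 = 31.0%
- k = 1: 33.58 / 86.02 = 39.0%
- k = 2: 43.61 / 96.05 = 45.4%

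The first detected case adds 8.0 points. Across the interval for VIA sensitivity the same step is +6.3 points (46.0% to 52.3%) at 0.54 and +9.4 points (19.0% to 28.4%) at 0.81.

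**One steered pick.** This differs from one more detected case, since CIN2+ cannot be seen before the speculum examination. The plan gives no CIN2+ prevalence in HPV-negative women, so one is assumed. Taking the 90% hr-HPV positivity in Section 6.3 and treating the 76 as the HPV-positive share gives 76 / 0.9 − 76 = 8.44 HPV-negative CIN2/3, or 8.44 / 812 = 1.04%. (Section 6.3 applies the 90% to the 76 itself, while Section 6.2 counts the 76 among HPV-positive women; hence this is an assumption.)

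- Unbiased expectation: (23.56 + 8.44) / (76 + 8.44) = 37.9%.
- One pick moved to a woman at twice average risk adds 0.0104 expected cases, weighted to 0.10: 32.10 / 84.54 = 38.0%, a shift of about 0.08 points. At five times average risk it is about 0.3 points.
- With assumed prevalence from 0.5% to 2% and risk ratio from 2 to 5, the shift is about 0.04 to 0.5 points.

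**Sustained selection.** If diseased women are r times as likely as others to be picked throughout, U = (23.56 + 8.44r) / (76 + 8.44r):

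- r = 0.5: 27.78 / 80.22 = 34.6%
- r = 1: 37.9%
- r = 2: 40.45 / 92.89 = 43.5%

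**Chance alone.** With k = 1 of 81, the exact 95% interval for HPV-negative prevalence is 0.03% to 6.7%, which puts corrected undertreatment between 31% and 60% even under perfect random sampling.

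**The case against.** A systematic sample of consecutive results, followed faithfully, can behave much like a random one. Section 6.3 already records the times that would fix the order, and Section 6.4 has real-time ODK entry with every form reviewed within 24 hours, so departures could be audited. Selections would also be sparse: over about 260 working days (an assumption for the 12 months in Section 4.1), 812 women is about 3 a day, or one selection every three days. With one arm there is no comparator to favour. The objective is secondary and described as largely descriptive, and chance error is large.

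Most of this stands and limits the point. But the audit is possible rather than planned, and no indicator counts HPV-negative women selected, examined or skipped. An interval can display chance error; it cannot display selection error.

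Two stronger readings are tempting. A reader might infer that one steered pick moves undertreatment by 8 points. It does so only if that pick changes whether a case is found, and on average the shift is well under 1 point. A reader might also infer that unblinded staff can see the count and reorder samples. The documents say nothing about who holds or sees the count or whether staff are blinded, and the remark on asynchronous assays describes the platform, not the clinic's workflow. Samples are also loaded before HPV status is known.

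**Conclusion.** The mismatch is real: selection is systematic and predictable, while the analysis calls it random and relies on "those who were referred to colposcopy were similar to those that were not" among women with the same test results. The documents show a risk of selection, not that any has occurred or will occur.

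Its potential size comes from the tenfold weight. One additional detected case moves corrected undertreatment from 31.0% to 39.0%, and sustained twofold selection in either direction would move the expected figure from 37.9% to 34.6% or 43.5%. That range needs steering on strong risk markers across all 81 picks, which no passage documents.

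The figures rest on VIA sensitivity of 0.69, on 8.4 HPV-negative CIN2/3, on 76 as the HPV-positive case count (a minimum, and CIN2/3 rather than CIN2+; more cases would shrink each shift), and on counting every VIA-missed case as undertreated.

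It would also be wrong to infer that the under-30% hypothesis is threatened. It concerns HPV-positive/VIA-negative women, so the HPV-negative sample does not enter it. The point is worth acting on because the remedy is nearly free.

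**What to change.** In Sections 4.2, 4.3 (Screening & Enrollment), 5.1 (footnote 3) and both places in Section 6.3 under secondary objective I, replace the count with a concealed, computer-generated 1-in-10 draw, made separately for HIV-positive and HIV-negative women. Show it in the existing ODK form only after the HPV-negative result has been entered and locked. A drawn woman counts as selected whether or not she is examined, and is not replaced.

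Log women drawn, examined and declined, and compare verified with unverified HPV-negative women on the baseline data already collected. Section 6.3 should state that the draw makes selection random but that missing at random still depends on drawn women who decline, because the correction uses those verified rather than those drawn.

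If the count is kept, Section 6.3 should call the sample systematic and define the order that counts as consecutive, and the same log and comparison should be added.

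The cost is a short amendment and one form field. Expected examinations stay at about 81. The number selected would vary by chance (SD √(812 × 0.1 × 0.9) = 8.5, about 9), and the clinic could not plan ahead for the next selected woman. The tenfold weight per case is unchanged.
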